The study will be a longitudinal, prospective, un-blinded, parallel-arm, multi-center, intention to treat, RCT, composed of centers with adult ECMO experience. Study subjects will include patients aged 18-65 admitted to these centers who are diagnosed with potentially reversible hypoxemic respiratory failure. Upon diagnosis with ARDS at the ECMO center, the components of the Murray score will be monitored every 2 hours. Once a Murray score >2.5 is obtained, the intensive care team will begin to profile the patient for the study and contact a study representative if the patient's consenting family member is willing to speak with them (the consenting family member will provide initial consent, then, once able the patient can choose whether or not to continue with the trial). Data collection for all study members will include demographics, diagnosis leading to ARDS, dates of hospitalization/ intubation/ extubation, dates of transfers/discharges, conditions at discharge, complications, cause of death, vent settings, blood gases, hemodynamic status, APACHE II, Murray lung score. Once a Murray score of 3.0 is obtained, the study subject will be randomized to conventional therapy or to ECMO. Given the large potential for other variables to significantly affect the primary outcome of mortality, randomization will be stratified in a fashion similar to that done in the CESAR trial. Stratification will be performed for age, hours of high P/high FiO₂, and number of organs failed (see Appendix 2).

Conventional therapy will include ARDSnet protocol vent management strategy with vent strategies guided by a pulmonologist. Data collection for the conventional management group will include time course, complications, and success with fulfillment of ARDSnet protocol (low-

volume, low-pressure with $P_{plat} < 30$). For the ECMO group, V-V ECMO with percutaneous cannulation will be used, with standardized lung rest vent settings (P_{pk} 20-25, P_{pl} 10-15, rate 10, FiO_2 30%), and ECMO will be continued until lung recovery is deemed obtained or until apparent irreversible multi-organ failure is attained. Data collection for the ECMO group will include cannulation information, flow, sweep, and pressure rates, and complications information.

c. Statistical Analysis:

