The estimated mortality for severe ARDS is 70% (NIH ARDS network database). As with the CESAR trial, an estimate of 10% severe disability in both trial arms will be used. For sample size calculation, Alpha will be set at 0.05 and Beta at 0.2. An effect size of a 25% proportional disability free survival benefit (70% mortality \rightarrow 52.5 mortality, or 17% difference in mortality) is estimated, which mirrors the effect size observed in the CESAR trial; using chi square testing this equates to a n of 132 patients for each study group.

C. Study procedures:

Intubation

All patients in this study will have respiratory failure prior to randomization, such that intubation and mechanical ventilation will occur prior to the study.

ECMO placement and maintenance

V-V ECMO will be placed for all patients randomized to the ECMO group. This requires a surgeon placing large catheters into the neck, in to the internal jugular vein, through a small incision. This is a simple, brief surgical procedure requiring sedation and anesthesia. Once the ECMO catheter has been placed, sedation will be used in order to prevent the patient from awakening and removing or moving the ECMO catheter, which is sutured in place in the neck. The catheters placed in the neck will extract blood from the heart that will then be run through the ECMO circuit for the purpose of oxygenating the blood and removing carbon dioxide from the blood. The ECMO circuits consist of pumps, membrane oxygenators, and filters. Blood running through the ECMO circuit has an increased risk of clotting such that all patients put on ECMO will receive heparin in order to avoid clotting. The heparin used to avoid clotting creates an increased risk of bleeding. To ensure that the therapeutic effect of heparin is appropriate, coagulation studies will be performed using simple blood tests.

D. Study Drugs: N/A

E. Medical Devices:

ECMO device

The ECMO circuit includes a Stockert SIII servo-controlled roller pump, Medtronic tubing, Medtronic .8meter squared membrane oxygenator, Medtronic ECMOTherm heat exchanger, a Stockert SIII control desk with dual pressure monitors, and Transonics Systems HT110 bypass

flow meter. Stockert—Freiburg, Germany; Medtronic—Minneapolis, MN; Transonics—Ithaca, NY.

Ventilator

Puritan Bennett 840 ventilators will be used.

F. Study Questionnaires:

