For the purpose of identifying the primary endpoint, a brief questionnaire will be completed via phone interview asking after the disability status of the patients 6 months after randomization. Two simple yes/no questions will be answered: is the patient bedbound? Is the patient able to dress and wash his/her self?

G. Study Subjects:

Patients for this study will include patients admitted by any means (either transferred patients or patients entering the hospital via the ED of the ECMO center hospitals) to the ECMO centers involved in the study. In all cases, ECMO will be initiated following randomization at the ECMO study center.

Inclusion criteria will include adult patients (18-65 yo) with severe but potentially reversible hypoxemic respiratory failure despite optimal conventional treatment at the same study centers providing ECMO. Respiratory failure as mentioned will be defined by Murray score >3.0

Exclusion criteria will include duration of high P (>30 cm Ppk) and/or high FiO₂ (>0.8) ventilation for >7 days, intra-cranial bleeding or any other absolute contraindications to heparinization, hypoxemic respiratory failure not fulfilling ARDS definition or hypoxemic respiratory failure deemed irreversible by a study consultant, moribund patients deemed to have minimal chance for survival regardless of chosen intervention as defined by a study consultant. ARDS related hypoxemic respiratory failure implies acute onset of a potentially reversible pathophysiology for which 'lung rest' allowing for low pressure/low FiO₂ vent settings may provide mortality benefit through avoidance of baro/volu-trauma and oxygen toxicity as well as avoidance of any degree of hypoxemia during the acute phase of disease; this is the rationale for excluding nonreversible and chronic hypoxemic respiratory failure.

H. Recruitment of Subjects:

As mentioned above, study subjects will be identified by ARDS diagnosis and by Murray score. Once an ARDS diagnosis is made, Murray score parameters will be monitored every 2 hours, and once Murray score is >2.5 , the patient's primary intensivist will then ask after the consenting family member as to the willingness to speak with a study representative.

I. Confidentiality of Study Data

A unique code will be created for each study participant for identification purposes and for data collection. Data will be secured in a secure location, only accessible by investigators.

J. Potential Conflict of Interest: Unknown.

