K. Location of Study: Studies will be conducted entirely within the critical care areas of participating ECMO centers.

L. Potential Risks:

All study subjects will be severely ill patients admitted to intensive care units and thus the risk of death and complications will be extremely high.

M. Potential Benefits:

A modernized high standard of intensive care will be provided to all subjects.

N. Alternative Therapies: N/A

O. Compensation to Subjects: none

P. Costs to Subjects: none

Q. Minors as Research Subjects: N/A

R. Radiation or Radioactive Substances: N/A

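### No by-arm review of accumulating deaths or complications, and no trial-level pause, is planned in an un-blinded trial of an invasive device with about 61% of patients expected to die

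*Protocol*

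**What the plan says.** - **Size.** Section B.c sets alpha at 0.05 and beta at 0.2, assumes mortality of 70% falling to 52.5%, and concludes: "using chi square testing this equates to a n of 132 patients for each study group". It mentions no look before the end.
- **Design.** Section B.b describes a "longitudinal, prospective, un-blinded, parallel-arm, multi-center, intention to treat, RCT".
- **Data collected.** The items for all patients in B.b include "dates of transfers/discharges, conditions at discharge, complications, cause of death, vent settings", and each arm has its own complications record. No one is assigned to compare these between arms.
- **Stopping.** The only stopping text, also in B.b, ends one patient's ECMO run: "ECMO will be continued until lung recovery is deemed obtained or until apparent irreversible multi-organ failure is attained".
- **Hazard.** Section C says: "The heparin used to avoid clotting creates an increased risk of bleeding". The coagulation tests there, and the exclusion in section G for contraindications to heparin, protect individual patients.
- **Risk.** Section L says "thus the risk of death and complications will be extremely high" and adds no monitoring plan.
- **Access.** Section I says: "Data will be secured in a secure location, only accessible by investigators".
- **Follow-up.** The only contact planned after discharge is in section F: "a brief questionnaire will be completed via phone interview asking after the disability status of the patients 6 months after randomization".

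**The concern.** When most patients are expected to die, each death on ECMO looks like an expected one. Each of several centers also sees only part of the 264 patients. An excess of deaths on ECMO would show only if someone pooled the centers and compared the arms, and the protocol asks no one to do so. Followed as written, it has no step that would interrupt randomisation before the 264th patient if ECMO were raising mortality.

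A boundary value may sit in an SAP or a committee charter. Who reviews deaths, when, and who may halt enrolment is a matter of trial conduct and patient protection. It belongs in a protocol written for an IRB, which already has sections on risk and data access.

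**Working it through.** **1. The plan's own figure.** Inputs from B.c: p1 = 0.70, p2 = 0.525, difference 0.175, mean 0.6125, alpha 0.05 (taken as two-sided), power 80%.

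- Uncorrected: n = [1.960·√(2 × 0.6125 × 0.3875) + 0.8416·√(0.70 × 0.30 + 0.525 × 0.475)]² / 0.175² = 120.5, so 121 per arm.
- Continuity-corrected: (n/4)·[1 + √(1 + 4/(n × 0.175))]² = 131.7, so 132 per arm.

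The stated 132 reproduces. It is a fixed-sample formula with no allowance for interim looks.

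**2. Deaths under the plan's assumptions.** 132 × 0.70 = 92.4 and 132 × 0.525 = 69.3. The total is 161.7 of 264, or 61%.

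**3. What a harm-only rule would do.** These inputs are assumptions, not from the protocol:

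- excess ECMO mortality of 5, 10, 15 or 20 points;
- control mortality at day 60 of 70%, 60% or 50% (the protocol gives 70% with no time point);
- looks at 44 and 88 patients per arm;
- 44 further patients enrolled while each look matures;
- a pause treated as permanent.

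The rule fires if the uncorrected pooled z, (pE − pC)/√[p̄(1 − p̄)·2/n], exceeds 1.960. Probabilities come from exact enumeration of the binomial counts. A pause after look 1 stops enrolment at 88 + 44 = 132, sparing 132 patients. A pause after look 2 stops it at 176 + 44 = 220, sparing 44. Half of those spared would have received ECMO, so:

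mean excess deaths averted = (132·P1 + 44·P2)/2 × excess

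Control mortality 70%, p<0.025:

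| Excess | Fires at look 1 (P1) | Fires at look 2 (P2) | Either | Excess deaths at full enrolment | Averted |
|---|---|---|---|---|---|
| 0 | 0.0265 | 0.0170 | 4.4% | 0 | 0 |
| 5 points | 0.0785 | 0.0711 | 15% | 6.6 | 0.3 |
| 10 points | 0.1963 | 0.1892 | 39% | 13.2 | 1.7 |
| 15 points | 0.4061 | 0.3022 | 71% | 19.8 | 5.0 |
| 20 points | 0.6821 | 0.2542 | 94% | 26.4 | 10.1 |

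Example at 10 points: (132 × 0.1963 + 44 × 0.1892)/2 × 0.10 = 34.2/2 × 0.10 = 1.7.

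**4. Sensitivity.**

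- Lower control mortality: at 10, 15 and 20 points the rule averts 1.5, 4.2 and 8.6 deaths (control 60%) or 1.3, 3.8 and 7.9 (control 50%).
- Stricter rule, p<0.01, control 70%: it averts 1.0, 3.6 and 8.6.
- Accrual, at a 10-point harm and control 70%: 2.1 deaths averted with 22 enrolling per look, 1.3 with 66, and 0.9 with 88, when look 2 comes too late to act. With 132 enrolling it is 0.4, and with 176 it is zero.

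**5. Cost to the trial.**

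- If ECMO is neutral, the rule pauses 4.1–4.4% of trials at p<0.025 and 1.8–1.9% at p<0.01, across the three control rates.
- At the planned 52.5% v 70% it fires in about 0.015% of trials.
- Power at 132 per arm is 83.7% by the uncorrected test and 80.3% by the continuity-corrected test that reproduces 132. The looks do not measurably change it.
- A harm-only pause cannot raise the false-positive rate for benefit.

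**The case against.** The strongest reply is that this is an omission, not an error. The sample size is right, only the protocol is at hand, and monitoring detail often sits in an SAP or charter. That holds for the exact threshold. It does not hold for whether anyone reviews deaths by arm and who may pause enrolment, which governs how patients are protected.

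The second reply is that the gain is modest and rests on assumed harms. This stands. At a 10-point harm with 70% control mortality the rule misses 61% of trials, and faster accrual shrinks the gain towards zero. The protocol's most recent adult evidence also favours referral to an ECMO center (63% v 47%), so harm is not the expected result. Section A does, however, report two older adult trials with no benefit and calls ECMO's role in adults unsettled.

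A reader might infer more than the document supports:

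- **That the protocol rules out interim looks.** It does not say so. A single stage is inferred from the fixed-sample calculation and the absence of any look.
- **That 70% mortality is expected throughout the trial.** It is the conventional-care assumption; the overall figure is about 61%.
- **That enrolment could not be paused.** Investigators are un-blinded and have the data, and section I does not stop them from reviewing it. They or an IRB could act ad hoc.
- **That 132 per arm is wrong.** It is not.

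**Conclusion.** The point holds as a worthwhile, low-cost safety improvement. No section plans a by-arm review of deaths or complications or a trial-level pause, and large harm from ECMO would meet no planned check before full enrolment. The benefit of the proposed rule is substantial only for large harm: about 5 of 19.8 excess deaths averted at 15 points and 10 of 26.4 at 20 points, against 1.7 of 13.2 at 10 points. These figures rest on 70% control mortality by day 60, 44 patients enrolling per look and a pause that becomes permanent, none of which the protocol states. The absence of the plan is certain; the size of the gain is not.

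**What to change.** Add to section B.c:

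> When each of the first 88, and later each of the first 176, randomised patients has died or reached day 60, a designated person who neither enrols nor treats trial patients tabulates, by assigned arm, deaths by day 60 from any cause and in any place, major bleeding, and cannulation complications. If ECMO-arm mortality is higher at one-sided p<0.025 by the uncorrected pooled two-proportion z test, randomisation pauses at all centers and the tables go to the overseeing IRB, or to a monitoring committee if one exists, which decides on resumption. The bleeding and cannulation tables go to that body at each look whether or not the rule fires. There is no early stop for benefit. The final test stays at alpha 0.05 with 132 per arm.

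A threshold of p<0.01 is an acceptable alternative. The test must be named, because a continuity-corrected or Fisher test raises each count below by one. ECMO deaths that fire the rule:

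| Per arm | Control deaths | p<0.025 | p<0.01 |
|---|---|---|---|
| 44 | 31 / 26 / 22 | 39 / 35 / 31 | 40 / 36 / 33 |
| 88 | 62 / 53 / 44 | 73 / 66 / 57 | 75 / 68 / 60 |

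Add date of death, vital status at day 60 and a major-bleeding item to the data collected. Add a clause to section I giving the designated person and the overseeing body access.

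Cost: one paragraph, one clause, three data items, one designated person, two tabulations, and the overseeing body's agreement to act. Patients discharged before day 60 need a record check or a short call. The downsides are about a 4% (or 2% at p<0.01) chance of an unnecessary pause if ECMO is neutral, and limited access to interim results by arm. No patients are added.

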Firstly, a multi-center trial RCT involving solely ECMO centers would allow for recruitment of sufficient patients for statistical power, and would remove the potential confounding variable of the type of center encountered in the CESAR trial. This would more clearly characterize a survival benefit provided by ECMO itself.

Secondly, the study population will be narrowed to include solely the first definition of respiratory failure employed in the CESAR trial (Murray score >3). The pH <7.2 definition of respiratory failure will be eliminated, as inclusion of patients meeting this parameter who may or may not meet the first parameter potentially diversifies the study group in terms of disease process and pathophysiology to an extent that is difficult to predict. This study will focus on severe ARDS alone as defined by a Murray score >3, with or without hypercapneic respiratory failure.

Hypothesis

For patients with severe but potentially reversible hypoxemic respiratory failure (Murray score >3) secondary to ARDS admitted to a center with ECMO, ECMO will increase survival without severe disability at 6 months post-randomization by a proportion of 25% as compared to non-ECMO ICU management at these same centers (including vent management by a pulmonologist as well as ARDSnet protocol).

Methods

a. Conceptual and Operational Definitions:

Study outcome will be a composite outcome of survival without severe disability at 6 months. Severe disability will be defined as being bed-bound and unable to wash and dress oneself.

b. Study Design

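### The disability component of the primary endpoint is collected by phone with no masking of the caller, and one joint question leaves some bed-bound patients unclassified

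*Protocol*

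**What the plan says.** Section B, Methods (a), sets the primary outcome: "Study outcome will be a composite outcome of survival without severe disability at 6 months". It then defines the non-fatal component: "Severe disability will be defined as being bed-bound and unable to wash and dress oneself".

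Section B, Methods (b), describes the trial as "longitudinal, prospective, un-blinded, parallel-arm, multi-center, intention to treat, RCT" and makes no exception for outcome assessment.

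Section F says how the disability status is obtained: "a brief questionnaire will be completed via phone interview asking after the disability status of the patients 6 months after randomization". Two items are asked, and the second is joint: "Two simple yes/no questions will be answered: is the patient bedbound? Is the patient able to dress and wash his/her self".

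The protocol does not say who calls, whether the caller knows the arm, whether the patient or a relative answers, or how a mixed answer on washing and dressing is recorded. It describes no adjudication. On handling of the data, section I says only this: "Data will be secured in a secure location, only accessible by investigators".

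**The concern.** Treatment in this trial cannot be blinded, but the 6-month call largely can be. Being bed-bound and being able to wash and dress are matters of judgement, reported by phone. If the caller knows the arm, borderline answers can be resolved differently in the two arms, and the difference goes straight into the primary comparison.

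The joint question adds a place where judgement is needed. Unable to wash and dress can mean unable to do either, or unable to manage the pair. For a bed-bound patient who can do one of the two, those readings give opposite classifications, and no rule chooses between them. The ambiguity is not arm-dependent in itself. It becomes so when the person who resolves it knows the allocation.

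The protocol itself fixes the design and wording of this instrument. A later analysis plan cannot restore masking after the calls are made, nor split an answer that was recorded as one yes or no.

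**Working it through.** **Which patients the joint question affects**

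| Bed-bound | Wash | Dress | Severe disability if it means unable to do either | If it means unable to do the pair | Literal answer to the joint item |
|---|---|---|---|---|---|
| no | any | any | no | no | irrelevant |
| yes | yes | yes | no | no | able |
| yes | no | no | yes | yes | not able |
| yes | one of the two only | | no | yes | not able |

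Only the last row is in dispute. The bed-bound item is also open to judgement and affects every borderline patient.

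**Inputs from section B, Methods (c)**

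- Control mortality 70%, ECMO mortality 52.5%.
- Severe disability 10% in both arms, denominator not stated.
- Alpha 0.05, power 80%, chi-square test, 132 per group.

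**The plan's own figure**

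With d = 0.175 and mean proportion 0.6125, the two-proportion formula is

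m = [1.96·√(2·0.6125·0.3875) + 0.8416·√(0.70·0.30 + 0.525·0.475)]² / 0.175² = 120.5, so 121.

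With continuity correction, n = (m/4)·[1 + √(1 + 4/(m·d))]² = 131.7, so 132.

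The stated 132 therefore reproduces from mortality alone, two-sided, with continuity correction. The protocol does not say which version of the test will be used in the analysis, so both are shown below.

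**How many patients can be reclassified, with no true effect and 70% mortality in both arms**

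- 10% of all randomized: 0.10 × 132 = 13.2 per arm. Failure rate 70% + 10% = 80%.
- 10% of survivors: 0.10 × 0.30 × 132 = 3.96 per arm. Failure rate 70% + 3% = 73%.

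**Effect on type I error**

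Suppose k disabled ECMO patients are recorded as not disabled. The control failure rate stays at p (80% or 73%), and the recorded ECMO rate is p − k/132. Let a and b be the recorded failures in the two arms. The test rejects when

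X² = 264·(a − b)² / [(a + b)(264 − a − b)] ≥ 3.84,

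with (|a − b| − 1)² in place of (a − b)² for the corrected test. The rejection probability is the sum of Bin(a; 132, p)·Bin(b; 132, p − k/132) over all rejecting pairs (a, b). The values of k are assumptions, since the documents give no misclassification rate.

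| Reading of the 10% | k | Shift, k/132 | Uncorrected | Corrected |
|---|---|---|---|---|
| All randomized (80% failure) | 0 | 0 | 5.0% | 3.4% |
| | 3 | 2.3 points | 7.4% | 5.3% |
| | 5 | 3.8 points | 11.6% | 8.8% |
| Survivors (73% failure) | 0 | 0 | 5.0% | 3.6% |
| | 2 | 1.5 points | 5.9% | 4.4% |
| | 4 | 3.0 points | 8.5% | 6.5% |

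The excess falls on one side. On the first reading with the uncorrected test, false rejections in favour of ECMO go from 2.5% at k = 0 to 6.6% at k = 3 and 11.2% at k = 5.

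**The case against.** Much can be said on the other side.

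- **Death dominates.** Of the 80 failure points expected in the control arm on the larger reading, 70 are deaths, which no caller can reclassify. A reader might infer from the composite wording that disability carries about equal weight. The plan's own figures do not support that. This limits the size of the problem.
- **No unmasked caller is named.** A reader might infer that the treating team makes the calls. The protocol does not say so. Section B, Methods (b), mentions a study representative, but only for the consent approach, and un-blinded there describes the trial as a whole. What stands is that nothing separates the caller from knowledge of the arm.
- **The joint question can be answered.** Taken literally, someone who can do only one of the two is not able to do both. That settles the answer but not the classification, because the definition in section B can be read the other way. The problem is confined to patients already reported bed-bound, probably few.
- **The size is assumed.** The values of k are all one way and in one arm. On the survivor reading with the corrected test, type I error stays below 5% at k = 2. Even the 3.8-point shift is small beside the planned 17.5-point effect.
- **A masked caller is a partial remedy.** Patients and relatives know the treatment and supply the answers. That is true, and respondent bias would remain.

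These arguments reduce the size of the concern. None of them supplies the missing safeguard or the missing rule.

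**Conclusion.** The point holds as a gap in how the smaller component of the primary endpoint is ascertained. The trial is declared un-blinded, the 6-month call has no masking, and the definition and the questionnaire do not settle how a bed-bound patient with a mixed answer counts.

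The size depends on two things that the protocol leaves open (the denominator of the 10% and the version of the test) and on an assumed number of misclassified patients. Over the cases computed, two-sided type I error ends between 4.4% and 11.6%, from a starting value of 3.4% to 5.0%. The exposure thus runs from negligible to material.

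The documents do not show that bias will occur, and they do not put the 132 per group in doubt on this account. The change is worth making before enrolment because it is cheap and cannot be made once the calls are done.

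**What to change.** 1. In section F, have existing study staff at a participating centre other than the treating one make the 6-month call. They are not told the allocation, and they use a fixed script that asks respondents not to reveal the treatment.
2. Replace the two questions with three separate yes/no items: bed-bound, able to wash, able to dress.
3. State in section B, Methods (a), and in section F the same combination of answers that counts as severe disability.
4. State who answers, patient or relative and in what order of preference, and apply that rule in both arms.

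The cost is some coordination between centres, a short script and one more question. No new staff are needed, and the sample size does not change. Some callers will still be unmasked by what respondents say. Because respondents know the allocation, the change reduces the bias without removing it.
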